Clinical data will be stored in the Clinical Data Warehouse (CDW) and in clinical research charts or research binders. Research charts or binders will be stored in locked filing cabinet, in a locked room at the NIDA-IRP. Imaging data are stored on a password protected drive on a UNIX server, which is maintained by the NRB. One copy of the consent form is kept in the participant's NIDA-IRP medical chart, the other is kept in a limited access, locked cabinet with other consent forms from the same protocol. Summaries of data analyses (e.g. demographics, clinical laboratory results, consent audit) are stored on a password protected shared NRB data drive. Participant data contained within files on the NRB data drive are identified by ARC number, and not by other personal identifiers such as name.

Plasma samples acquired for measurement of cortisol and ACTH, will be destroyed once valid assays have been obtained.

Principal Investigator: [name].

6. Data Sharing Plan

Unless specified otherwise, data collected in this study may also be combined with data collected across IRB approved protocols, including the NRB Repository Protocol, 06-DA-N802 and the NRB protocol, 10-DAN-457, "Characterization of Phenotypic and Genotypic Regressors to allow for greater power to detect otherwise small effect size analyses untestable with a single data set. Additionally, de-identified data may be shared with properly administered databases and/or with collaborators with whom proper data sharing agreements are in place.

Date: March 2, 2022

7. Additional Considerations

N/A

8. Risks/ discomforts

8.1. Questionnaire and Characterization Measures.

The questions asked may be perceived as embarrassing or may cause anxiety or distress. Nevertheless, such reactions are expected to be temporary and to rapidly dissipate spontaneously.

Risk Minimization. Participants will be advised prior to completing these measures that they may refuse to answer any questions that cause them discomfort. Furthermore, any participant who experiences anxiety or distress as a result of these assessments will be able to speak to a NIDA-IRP mental health professional to discuss this.

8.2. Nicotine Patch Administration.

Adverse events (AEs) related to the nicotine patch include:

- Abdominal Pain
- Chest pain
- Coughing
- Diaphoresis
- Dizziness
- Dry mouth
- Headache

- Palpitations
- Rash
- Restlessness
- Sleepiness
- Temporary mood change
- Minor skin irritation
- Nausea/Vomiting

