The most common possible side effects of nicotine patch administration are skin irritation, sleep disturbances, and nausea and vomiting. All effects are temporary and will dissipate spontaneously and quickly (1-2 hrs) after patch removal.

More severe toxic effects of nicotine may include cardiac tachyarrythmias, hypertensive crisis, dizziness, weakness, confusion, and convulsions. The lethal dose of nicotine in adults is from 0.5-1.0 mg/kg or a total single bolus dose of 40-60mg (http://www.cdc.gov/mmwr/preview/mmwrhtml/mm5218a3.htm) (US-EPA. Chemical

Principal Investigator: [name].

profile: Nicotine. US Environmental protection Agency 1987). Nicotine death may likely result from paralysis of respiratory muscles or central respiratory failure. Individuals likely have widely different levels of tolerance to the toxic effects of nicotine based on previous exposure. Nicotine patch doses up to 63mg/d have been shown to be safe and generally well-tolerated by smokers (Zevin et al., 1998; Ebbert et al., 2007). Most reports of nicotine poisonings and deaths are typically the result of contact with nicotine-containing pesticides (Benowitz et al., 1987). Although ingestion of nicotine is common, deaths due to poisoning are extremely rare, due to early vomiting and the short half-life of the drug. In the current protocol, the protracted release of nicotine via the transdermal (24hr) patch should keep nicotine plasma concentrations well within a safe range. If participants show initial signs of nicotine poisoning during the patch-toleration test (i.e., burning throat, nausea, vomiting) they may be excluded from further participation depending on the severity of their symptoms

Date: March 2, 2022

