8.4. Smoking abstinence/nicotine deprivation

The 36 hr nicotine deprivation is expected to produce acute nicotine withdrawal symptoms, and hence some degree of discomfort. According to the DSM-IV (APA, 1994) acute nicotine withdrawal is associated with the following symptoms:

- dysphoric or depressed mood
- insomnia
- irritability, frustration, or anger
- anxiety
- difficulty concentrating
- restlessness
- decreased heart rate
- increased appetite

As our primary interest in the current protocol is the neurobiological mechanisms underlying acute nicotine withdrawal symptoms, no specific efforts will be made to minimize the discomfort associated with these

Principal Investigator: [name].

symptoms during the participant's abstinence period or scanning session. However, participants will be fully aware that their participation is voluntary and that they can withdraw from the study at any time, including during the abstinence period or scanning session.

Date: March 2, 2022

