Date: March 2, 2022

Some of these questionnaires are also found in NIDA-IRP protocol 10-DA-N457. If the participant has enrolled in 10-DA-N457, these questionnaires may be completed within that protocol instead. These include: Fagerstrom Test for Nicotine Dependence, Toronto Alexithymia Scale (TAS-20), Adult ADHD Self-Report Scale, Positive and Negative Affect Schedule, and the State-Trait Anxiety Inventory Form Y (STAI). Questionnaires answered during screening, under Protocol 415, may also be included for analysis. Questionnaires do not need to be repeated on visit days if they were conducted during either the screening Protocol 415 or Protocol 457.

Nicotine Dependence and Withdrawal Scales (Smoking Group Only).

- 1) **The Fagerström Test for Nicotine Dependence** (Heatherton et al., 1991) is a six item test that measures the severity of nicotine addiction on a 0-10 scale. To be completed once (Trait). Completion time: ~2-3min.
- 2) The Tobacco Craving Questionnaire (Singleton et al., 2003) is a brief instrument used to assess current feelings related to smoking and craving using 12 Likert-type items. Each item is rated on a 7-point scale from strongly disagree to strongly agree. To be completed each visit (State). Completion time: ~2min.
- 3) **Tobacco Craving Scale** consists of 5 self-report items pertaining to desire for a cigarette that are rated on a 10-point scales. To be completed each visit (State). Completion time: ~2 min.
- 4) The Minnesota Nicotine Withdrawal scale (Hughes and Hatsukami, 1998) yields a measure of total withdrawal related discomfort based on ratings from 15 self-report items. To be completed each visit (State). Completion time: ~2-3 min.
- 5) **The Cigarette Dependence Scale** (Etter et al., 2003) is a brief 12-item self report that assesses the main components of DSM-IV and ICD-10 definitions of dependence, which include compulsion, withdrawal symptoms, loss of control, time allocation, neglect of other activities, and persistence despite harm. To be completed once (Trait). Completion time: ~2-3min.
- 6) A **general smoking history questionnaire** will also be administered. To be completed once (Trait). Completion time: ~5 min.

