24.10. Risks/discomforts

tDCS: tDCS is a minimal risk procedure and side effects are mild, benign and transient. These may include itching, tingling, a reddening or a burning sensation of the skin underneath the stimulating electrode. These symptoms are deemed a discomfort in 10-14% of tDCS participants (Brunoni et al 2011). In order to further reduce these minimal risks, the impedance of the tDCS system will be continuously monitored throughout all sessions. Instead of the more popular sponge pads soaked in saline, bicarbon electrodes with a thick layer of conductive paste will be used to prevent drying of the electrodes during the scanning session. The stimulator will automatically turn off when the impedance value exceeds the critical range.

If discomforts occur, a decision will be made by the MAI or designate about whether the participant should complete the experiment. Headaches can also be a side effect of tDCS, and these subside with removal of the strap or with non-prescription medication. Non-prescription pain killers will be provided as decided on a case-by-case basis by the MAI.

Nicotine patch: the risks/discomforts of the nicotine patch are the same as listed in *Section 8.2. Nicotine Patch Administration*. Only the smoker group will receive nicotine patches. Nicotine dose will be individually tailored based on the average number of cigarettes smoked per day to better match daily nicotine intake. The following graded dosing scale will be used to individually tailor nicotine dose, it is identical to the scale found in *Section 4.1, Study Overview*:

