CDW Entry (for investigator entry):

TLFB - Tobacco Cigarettes

Date of Last Visit:
Enter the number of cigarettes smoked per day since the last session, starting with
resterday and working backwards

Day 1 (yesterday)

Day 2

Day 3

Etc...

*#+9) Perceived Stress Scale (PSS; Cohen, Kamarck, & Mermelstein, 1983). The PSS is a brief instrument used to assess degree of perceived stress during the past month using 10 Likert-type items. Each item is rated on a 5-point scale from never to very often. Completion time: ~5min.

The questions in this scale ask you about your feelings and thoughts **during the last month**. In each case, you will be asked to indicate by circling *how often* you felt or thought a certain way.

0 = Never 1 = Almost Never 2 = Sometimes 3 = Fairly Often 4 = Very Often 1. In the last month, how often have you been upset 2. In the last month, how often have you felt that you were unable 4 3. In the last month, how often have you felt nervous and "stressed"? 0 1 2 3 4 4. In the last month, how often have you felt confident about your ability to handle your personal problems? 0 1 2 3 4 5. In the last month, how often have you felt that things 6. In the last month, how often have you found that you could not cope 7. In the last month, how often have you been able 4 8. In the last month, how often have you felt that you were on top of things?.... 0 1 2 34 9. In the last month, how often have you been angered 10. In the last month, how often have you felt difficulties

tDCS Arm Questionnaires

Date: March 2, 2022

The Minnesota Nicotine Withdrawal scale (Hughes and Hatsukami, 1998) yields a measure of total withdrawal related discomfort based on ratings from 15 self-report items. Completion time: ~5 min.

Directions: Please rate the degree to which you have experienced the following, over the past 24 hrs.

0=none, 1=slight, 2=mild, 3=moderate, 4=severe

1) Angry, Irritable, frustrated	0 1 2 3 4
2) Anxious, Nervous	0 1 2 3 4
3) Depressed mood, Sad	0 1 2 3 4
4) Desire or craving to smoke	0 1 2 3 4
5) Difficulty concentrating	0 1 2 3 4
6) Increased appetite	01234
7) Insomnia, sleep problems, awakening at night	0 1 2 3 4
8) Restless	0 1 2 3 4
9) Impatient	0 1 2 3 4
10) Constipation	0 1 2 3 4
11) Dizziness	0 1 2 3 4
12) Coughing	01234
13) Dreaming or Nightmares	0 1 2 3 4
14) Nausea	0 1 2 3 4
15) Sore throat	0 1 2 3 4

Date: March 2, 2022

Principal Investigator: [name].

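### The tDCS arm's 15-item withdrawal total includes nausea and coughing, which the protocol lists as patch side effects, so the nicotine-versus-placebo contrast on it can be diluted

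*Combined protocol and SAP*

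**What the plan says.** Section 24.6 (Characterization Measures) and the tDCS questionnaires in Appendix 4 both describe the Minnesota scale as one that "yields a measure of total withdrawal related discomfort based on ratings from 15 self-report items". It is a state measure for smokers, completed at each visit, so it is taken on both the nicotine-patch day and the placebo-patch day. Each item is rated "0=none, 1=slight, 2=mild, 3=moderate, 4=severe", under the instruction "Please rate the degree to which you have experienced the following, over the past 24 hrs". Items 11, 12 and 14 are dizziness, coughing and nausea. No subscale, item exclusion or scoring formula is given.

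Section 8.2 introduces its list with "Adverse events (AEs) related to the nicotine patch include"; coughing, dizziness, restlessness, temporary mood change and nausea/vomiting are on it. It adds: "The most common possible side effects of nicotine patch administration are skin irritation, sleep disturbances, and nausea and vomiting". Section 24.10 carries this into the tDCS arm: "the risks/discomforts of the nicotine patch are the same as listed in" Section 8.2. The arm's patch instructions (Appendix 12) also name dizziness and upset stomach.

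On the other side, Section 8.4 states that "acute nicotine withdrawal is associated with the following symptoms" and lists eight. Nausea, coughing and dizziness are not among them.

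Self-reported craving, withdrawal and mood form primary outcome 3 in Section 10.1. There they serve as regressors for BOLD data and as the main check that the withdrawal manipulation worked. Sections 24.11 and 24.12 adopt the main protocol's outcomes and analyses for the tDCS arm.

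**The concern.** The nicotine patch is there to keep withdrawal low in the sated condition, so the withdrawal score should be lower on the nicotine day than on the placebo day. If the patch also causes some nausea or coughing, those items move the other way and are added into the same total. The contrast then estimates withdrawal relief minus patch side effects and leans towards no difference. The same mixture would enter any regression of BOLD change on the total.

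This is particular to the tDCS arm. The Wisconsin scale used in the Main Study (Appendix 4, 28 items) asks about none of the three symptoms.

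**Working it through.** **Plan's own figure.** Appendix 4 prints 15 items, as stated. At 0-4 each, a sum runs to 15 x 4 = 60. The text says total without a formula, so a sum is assumed here; a mean would have the same problem.

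**Items against the withdrawal list in Section 8.4.**
- Matching: 1 (angry/irritable), 2 (anxious), 3 (depressed), 5 (concentration), 6 (appetite), 7 (insomnia), 8 (restless). That is seven items.
- Not matching: 4 (craving), 9 (impatient), 10 (constipation), 11 (dizziness), 12 (coughing), 13 (dreaming/nightmares), 14 (nausea), 15 (sore throat). That is 15 - 7 = 8 items, or 8 x 4 = 32 of 60 points.

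**Items against the arm's visual analog list of withdrawal symptoms (Section 24.6 and Appendix 4).** That list covers desire to smoke, impatience and dizziness, which accounts for items 4, 9 and 11. Items 10, 12, 13, 14 and 15 stay outside both lists: 5 items, or 5 x 4 = 20 points.

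**Items against the patch effects in Section 8.2.**
- Patch effect and in neither withdrawal list: 12 and 14. That is 2 x 4 = 8 of 60 points (13%).
- Patch effect and also in the visual analog list: 11. Adding it gives 3 x 4 = 12 of 60 points (20%).
- Patch effect and also in Section 8.4: 8 (restlessness). Sleep disturbance and temporary mood change in Section 8.2 likewise overlap item 7 and the mood items.

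**What this does to the contrast.** Let nicotine lower each of items 1-9 by a mean of r points and raise each of k side-effect items by a mean of s points, with the remaining items unchanged. The nicotine-minus-placebo difference on the total is -9r + ks, against -9r on items 1-9. The share of the contrast lost is ks/(9r).

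The documents give neither r nor s. With r = 0.5 assumed, 9r = 4.5 and:
- s = 0: nothing is lost.
- s = 0.25: 0.5/4.5 = 11% for k = 2 (nausea, coughing); 0.75/4.5 = 17% for k = 3 (with dizziness).
- s = 0.5: 1.0/4.5 = 22% for k = 2; 1.5/4.5 = 33% for k = 3.

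These values show how the mechanism works. They are not estimates, and zero is as compatible with the documents as any other value.

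**Exposure when the scale is filled in.** The study patch goes on about 2 hours before the first session. Questionnaires may be given before, between or after scans on a visit of about 8 hours (Section 24.6). Patched time within the 24-hour recall is therefore about 2 hours or less for an early rating, and at most roughly 2 + 8 = 10 hours for a late one.

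**The case against.** **Little patch effect is to be expected.** Doses are matched to daily smoking, participants first wear a test patch, and most of the recall window precedes the study patch. This stands as a reason to expect a small absolute rise. It does not settle the matter: exclusion after signs of intolerance is discretionary in Section 8.2, and a recall window that dilutes side effects dilutes withdrawal relief too.

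**The 15-item total is not the named outcome.** Section 10.1 names no scale or score. Smokers also complete two craving scales, the withdrawal visual analog items, the affect and mood scales and state anxiety at each visit, and the hypotheses in Section 24.3 concern connectivity, BOLD and task performance. This stands and limits the consequence to one of several symptom measures. It also shows the gap: where no score is specified, the described total is the natural default.

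**The protocol treats dizziness as withdrawal too.** This is correct. Dizziness cannot be counted as a pure side effect; its sign is ambiguous, which is still a reason to look at it separately.

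**Scoring may be settled in the cited reference for the scale.** That source is not part of the documents, and the plan does not state such a rule. Items are rated one by one, so any scoring remains possible.

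**A subset of items 1-9 is not clean.** This is also correct: restlessness, sleep and mood items overlap patch effects. The subset lessens the overlap without ending it.

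**Conclusion.** The point holds as a minor one. The described total contains two items that the protocol treats as patch effects and places in no other withdrawal list (8 of 60 points), and a third whose direction is ambiguous (12 of 60 together). A patch contrast on the total can be diluted towards no difference. The conclusion rests on the total being used for that contrast and on the patch causing some of these symptoms in this sample; the size is unknown and may be small.

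Stronger readings may tempt a reader, but the documents do not support them:
- That a sixth to a third of the contrast is lost. Those figures depend wholly on assumed item changes.
- That the bias is greatest at the highest patch doses. Those go to the heaviest smokers, and Section 8.2 ties tolerance to previous exposure. No dose gradient is given, and nicotine dose is already a covariate in the Section 11.2 model that this arm adopts.
- That the arm's manipulation check fails. Other craving, withdrawal and mood scales are available for it.

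**What to change.** Before unblinding, state which Minnesota score is used for the nicotine-versus-placebo contrast and for any BOLD regression. Use either items 1-9 (range 0 to 9 x 4 = 36) or the seven items that match Section 8.4 (items 1, 2, 3, 5, 6, 7 and 8; range 0 to 7 x 4 = 28) with craving analysed separately. Report items 10-15 individually by patch condition, and keep the 15-item total as a sensitivity display.

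The cost is a scoring rule in the analysis plan: no new data, visits or participants. There are two small downsides. The subset departs from the total that the protocol describes, which the sensitivity display covers. It also still holds restlessness, sleep and mood items that overlap patch effects, so the report should say that contamination is reduced and not removed.

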10.1. Primary outcomes measures

1) Change in BOLD signal and FC related to task parameters, between drug conditions: will provide important insight into the neurobiological mechanisms underlying acute nicotine withdrawal, in particular those related to anhedonia, negative affect, inhibitory control and impulsive decision making.

Date: March 2, 2022

- 2) Behavioral performance on each of the tasks assessing inhibitory control processes, reward responsiveness, amygdala, striatal, BNST reactivity and impulsive decision making (e.g., reaction time, error rate, hit rate, reward bias): will provide task-related parameters necessary for analysis of BOLD data. Performance data will function as a secondary outcome by providing behavioral validation of acute nicotine withdrawal effects.
- 3) Self-reported craving, withdrawal symptoms and mood/affect: will be employed as regressors in the analysis of task and resting BOLD data. They will also provide the primary means of validating the acute nicotine withdrawal manipulation.
- 4) Smoking status at 1, 6 and 12 months: Smoking status (relapse vs abstinent) at each of the follow-up time points will be based on 7-day point prevalence defined as no smoking (not even a puff) or use of any tobacco products for the past 7 days. This is a standard method of assessing abstinence and dichotomizing relapse status at follow-up (Keating & Siddiqui, 2006; Leventhal et al., 2008; Swan et al., 2010b). Whenever abstinence at follow-up is assessed in-person, self-reported abstinence will be corroborated with breath CO and urine cotinine levels.

10.2. Secondary outcome measures include:

- 4) MRS for glutamate concentration: Glutamate concentration at the PFC and hippocampus is expected to change as a function of acute nicotine withdrawal and may also play a role in the expected reduction in VS reactivity and anhedonia.
- 5) Plasma ACTH and cortisol: are expected to increase as a function of acute nicotine withdrawal and is expected to play role in both anhedonia and negative affective symptoms, potentially by acting at the amygdala, BNST and VS.
- 6) Resting state CBF from ASL: To test for changes in neural activity (i.e., not connectivity) at rest it is necessary to employ a measure which does not require a baseline. CBF provides such a measure as changes in blood flow are referenced to a common arterial location outside of the brain.

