The MRI/tDCS visit day will last approximately 8 hours, with the three MRI/tDCS sessions separated by an interscan break of about 40-60 minutes, accounting for an approximate 1.5 hour break between tDCS sessions ("Inter-tDCS interval", **Figure 3**).

Before beginning the MRI/tDCS visit days, all subjects will attend a half day orientation visit. This time will consist of an informed consent session, nurse assessment, task training, mock scanner session, and tDCS toleration test (described below). Questionnaires will also be administered during this time. If subjects cannot complete questionnaires on this day, they can finish them at a later visit. The visit will last about 4.5-5.5 hours. Some participants may take longer to answer questionnaires, complete training tasks, or other procedures, and in this case their visit would be extended. If structural scans are added to orientation day (see note on next page), the day will be extended by about 30-45 minutes. Additional time or scans on orientation day will be included in compensation according to the remuneration table.

tDCS toleration test: Participants will experience tDCS during the orientation session using the ramp up that they will experience during tDCS sessions to make sure they tolerate the sensation. This will last long enough for them to get the full strength (2mA intensity) and to decide if they want to proceed with the experiment, i.e. generally less than 2 minutes but not more than 5 minutes. During the toleration test, the participant will be

CNS IRB Protocol Template (rev. 16Jun11)

Principal Investigator: [name].

seated comfortably in a chair outside the scanner (mock or real) environment. This brief tDCS application allows the participant to experience tDCS in a comfortable environment prior to receiving tDCS in the scanner, ask further questions, and decide whether they wish to participate further in the study.

Date: March 2, 2022

The MRI/tDCS visit days will consist of a brief nurse visit, refresher training on fMRI tasks, and the 3 MRI/tDCS scanning sessions. Questionnaires will also be administered on this day, prior to scanning, during the inter-scan breaks, and/or after the scans. The day will last about 8 hours.

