Smoker participants will be given nicotine patches during the study. One of these patches will be a Nicotine Tolerance Test Patch (see Appendix 12), and will be applied by the nurse at the orientation session. The other two will be blinded Study Patches containing either nicotine or placebo. The Study Patches should be applied 2 hours prior to the first MRI/tDCS session, due to the pharmacokinetic profile of nicotine. Smoking participants will be given blinded study patches (Study Patch 1, Study Patch 2) to apply the morning of the MRI-tDCS sessions, along with an instruction sheet for how to use the patches (see Appendix 12).

Smokers will attend 1 Orientation visit (half-day) and 2 MRI/tDCS visits (full days), for a total of 3 visit days (**Figure 1A**). Smokers will need to abstain for 12 hours prior to the MRI/tDCS visit days. All 3 tDCS conditions will be applied during each MRI/tDCS visit day. One MRI/tDCS visit day will be completed with a patch containing nicotine, and the second MRI/tDCS visit day will be completed with a patch containing placebo. On the morning of their first imaging day, smokers will apply Study Patch 1. The content of the patch (nicotine or placebo) will be randomized and double-blinded. The subject will apply Study Patch 2 on the morning of their second MRI/tDCS visit day.

Non-smokers will attend 1 Orientation visit (half-day) and 1 MRI/tDCS visit day (full day) (**Figure 1B**), without nicotine or placebo patch conditions. All 3 tDCS conditions will be applied during the MRI/tDCS visit day. Non-smokers will be matched by age, gender, race, and education, as recruitment allows.

To assess the online and after-effects of tDCS on the ECN, DMN and SN, the MRI/tDCS session will measure resting state functional connectivity, and BOLD signal and behavioral performance during cognitive fMRI tasks. Three classical behavioral tasks will be presented during the scanning session: (1) Parametric Flanker Task known to elicit activity from the ECN and SN, (2) N-back task known to target the ECN, and (3) Amygdala Reactivity Task, known to be modulated by the SN and DMN. (See Section 24.8 for task details). An example of an MRI/tDCS session timeline is shown in Figure 2, the exact order of tasks may differ across participants.

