Please rate how strong your desire for a cigarette is right now.

No desire
Extremely strong
0 1 2 3 4 5 6 7 8 9 10

Please rate how strong your desire for a cigarette was during the last 24 hours.

No desire
Extremely strong
0 1 2 3 4 5 6 7 8 9 10

Please rate how often you had the urge to smoke during the past 24 hours.

Not at all Extremely often 0 1 2 3 4 5 6 7 8 9 10

In the past 24 hours, please rate how strong your urges have been for a cigarette when something in the environment has reminded you of it.

No urges
Extremely strong
0 1 2 3 4 5 6 7 8 9 10

Please imagine yourself in the environment in which you previously used drugs and/or alcohol. If you were in this environment right now, what is the likelihood that you would smoke?

Not at all Sure I would use 0 1 2 3 4 5 6 7 8 9 10

Principal Investigator: [name].

*#+3) Wisconsin Smoking Withdrawal Scale (WSWS) is a 28-item scale that measures the severity of smoking withdrawal symptoms.

Date: March 2, 2022

Please answer the following questions based on how you have felt or what you have noticed over the last 24 hours. Answer based on how you have felt in general during this time.

0	1	2	3	4
Strongly	Disagree	Feel neutral	Agree	Strongly agree
disagree				

- 1. Food is not particularly appealing to me
- 2. I am getting restful sleep
- 3. I have been tense or anxious
- 4. My level of concentration is excellent
- 5. I awaken from sleep frequently during the night
- 6. I have felt impatient
- 7. I have felt upbeat and optimistic
- 8. I have found myself worrying about my problems
- 9. I have had frequent urges to smoke
- 10. I have felt calm lately
- 11. I have been bothered by the desire to smoke a cigarette
- 12. I have felt sad or depressed
- 13. I have been irritable, easily angered
- 14. I want to nibble on snacks or sweets
- 15. I have been bothered by negative moods such as anger, frustration, and irritability
- 16. I have been eating a lot.
- 17. I am satisfied with my sleep
- 18. I have felt frustrated
- 19. I have felt hopeless or discouraged
- 20. I have thought about smoking a lot.
- 21. I have felt hungry
- 22. I feel that I am getting enough sleep.
- 23. It is hard to pay attention to things
- 24. I have felt happy and content
- 25. My sleep has been troubled
- 26. I have trouble getting cigarettes off my mind
- 27. It has been difficult to think clearly.
- 28. I think about food a lot.

Principal Investigator: [name].

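### In the tDCS arm, 24-hour recall items dilute the nicotine versus placebo patch contrast, and a per-visit score at no fixed time cannot be assigned to a tDCS condition

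*Combined protocol and SAP*

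**What the plan says.** Section 24.6 gives smokers two MRI/tDCS days, one on a nicotine patch and one on placebo, each after 12 h without smoking. On timing it states: "The Study Patches should be applied 2 hours prior to the first MRI/tDCS session". It also states: "All 3 tDCS conditions will be applied during each MRI/tDCS visit day", with about 90 minutes between stimulations.

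The same section says the Minnesota scale "yields a measure of total withdrawal related discomfort based on ratings from 15 self-report items. To be completed each visit (State" (the bracket, which closes after that word, marks it as a state measure). The craving, mood and state-anxiety scales have the same each-visit schedule. The time of day is left open: "Questionnaires will also be administered on this day, prior to scanning, during the inter-scan breaks, and/or after the scans".

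In Appendix 4, the instruction on the tDCS-arm Minnesota form is: "Please rate the degree to which you have experienced the following, over the past 24 hrs". The Tobacco Craving Scale in that appendix has five items, and three of them look back 24 h, for example: "Please rate how strong your desire for a cigarette was during the last 24 hours".

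Section 24.11 takes the arm's outcomes from Sections 10.1 and 10.2. Section 10.1 lists self-reported craving, withdrawal and mood as the third primary outcome and gives them two uses. They are regressors for the BOLD data, and: "They will also provide the primary means of validating the acute nicotine withdrawal manipulation".

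**The concern.** The recall window and the manipulations cover different hours. Both patch visits share the previous day's usual smoking and a stretch of abstinence without a patch, and most of the 24 h window records that shared time. A small patch difference on these items could be taken as weak withdrawal when much of it is dilution. Two participants with the same response could also score differently because one filled in the form before scanning and the other after the last scan.

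The check matters in this arm. The Main Study draws plasma nicotine (Section 4.4), but the tDCS-arm nurse assessments list none. Expired CO shows only that the participant did not smoke, which is required under both patches.

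For stimulation the problem is attribution. If anodal, cathodal and sham all occur within the visit that a score describes, that score belongs to none of them.

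**Working it through.** **The plan's own figure.** There is no stated figure on recall timing. The arm's sample size (Section 24.12: 34 per group, matched-pairs t-test, two-sided 0.05, power 0.8, medium effect) reproduces. With d = 0.5 a noncentral-t calculation gives n = 34 with power 0.808. It is not in dispute.

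**Inputs.** Recall window 24 h (Appendix 4); patch about 2 h before the first session and 12 h abstinence (Section 24.6, Appendix 12); visit about 8 h, stimulation about 25 min, interval about 90 min (Section 24.6); 35 smokers expected to complete (Section 24.12).

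**The window just before session 1.** It holds 2 h on patch, about 10-12 h of abstinence without a patch, and about 10-12 h of usual smoking, 24 h in all. Only the 2 h can differ between visits.

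**Share of the window that differs** = hours on patch / 24:
- before session 1: 2/24 = 8%
- end of an 8 h visit, patch applied on arrival: 8/24 = 33%
- end of an 8 h visit, patch applied 2 h before arrival: (2 + 8)/24 = 42%

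**Illustration of the effect.** Assume that respondents average evenly over the window, that the patch acts fully from placement, that the SD of differences is unchanged, and that a present-moment rating would show d = 0.5. Then observed d = 0.5 x share. Power is for a two-sided paired t-test with n = 35.

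| Hours on patch | Share | Observed d | Power |
|---|---|---|---|
| 2 | 8% | 0.04 | 6% |
| 6 | 25% | 0.13 | 11% |
| 8 | 33% | 0.17 | 16% |
| 10 | 42% | 0.21 | 22% |
| present-moment rating | 100% | 0.50 | 82% |

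Section 11.4 cites d = 0.15 to 0.52 for self-report after 8 h deprivation. Over that range the observed d would be 0.15 x 2/24 = 0.01 to 0.52 x 2/24 = 0.04 before session 1, and 0.15 x 10/24 = 0.06 to 0.52 x 10/24 = 0.22 late in the day. If respondents in fact answer for the present moment, the dilution disappears, so the last row of the table is the other bound.

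**tDCS.** One stimulation fills 25/1440 = 1.7% of the window, and all three fill 75/1440 = 5.2%. Repeating the 24 h form after each session would not help. Equivalent points in successive sessions are about 90 + 25 = 115 min apart, so successive windows would overlap by (1440 - 115)/1440 = 92%.

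**The case against.** The case for leaving the plan alone has real force.

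- **Patch.** A reader might infer that the Minnesota scale cannot register the patch at all. The documents do not support that. Nicotine and placebo fall on different visit days, so each has its own score, and the effect is diluted rather than removed.
- **Other instruments.** A reader might infer that the arm has no self-report check of withdrawal. It has several. The 12-item Tobacco Craving Questionnaire, PANAS, POMS, the state form of the STAI and two Tobacco Craving Scale items ask about the present. The 100 mm visual analog scale covers withdrawal symptoms and prints no recall window.
- **tDCS.** A reader might infer that a planned active-versus-sham test of withdrawal is lost. The hypotheses in Section 24.3 concern connectivity, BOLD signal and task performance; only the arm's title points to relief of withdrawal.
- **Schedule.** The text says each visit, not once per visit, and sessions may exceptionally be split across days.

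All of this stands, and it limits the point. It does not remove it: the completion time is still open, and the present-moment scales share the per-visit schedule, so they cannot be tied to a tDCS condition either.

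Two extensions fail. Scoring only Minnesota items 1-9 would not remove patch side effects, because Section 8.2 also lists restlessness and temporary mood change. The Perceived Stress Scale is "used to assess degree of perceived stress during the past month using 10 Likert-type items", but no section assigns it to the deprived versus non-deprived contrast.

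**Conclusion.** The concern holds in limited form. On the 24 h items the patch contrast is diluted to between about 8% and 42% of the window, depending on an unfixed completion time. On the standard schedule, no per-visit score from any state scale can be assigned to a tDCS condition.

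The shares follow from the documents' approximate timings. The translation into d of about 0.04 to 0.21, and power of 6% to 22%, rests on the assumptions stated with the table, which the documents neither support nor contradict. It shows how much could be lost and is not a forecast.

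The arm's connectivity, BOLD and behavioral hypotheses are unaffected. This is a cheap improvement to a manipulation check and a primary self-report outcome, and it is worth making.

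**What to change.** On MRI/tDCS visit days:

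1. Word the Minnesota scale and the three 24 h Tobacco Craving Scale items for *right now*. Leave out Minnesota items 7 (sleep) and 13 (dreams), which cannot be rated for the present moment.
2. Give the Minnesota scale and the 12-item Tobacco Craving Questionnaire at fixed times: on patch before the first session, and immediately after each of the three tDCS sessions.
3. State in Section 24.12 that the pre-session score serves the patch check and the post-session scores serve any tDCS contrast. If no tDCS contrast on self-report is intended, say so; the pre-session rating is then enough.

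**Cost.** Section 24.6 puts the two forms at about 2 and 2-3 minutes, so about 5 extra minutes per session. Appendix 4 gives longer times (10 and 5 minutes, 15 together), which would still fit the 40-60 minute breaks; the rating after the third session falls at the end of the day. Visit-day Minnesota scores would no longer be comparable with the 24 h version.
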